1.0 Objectives / Specific Aims

The overall aim of this proposed effort is to test transcutaneous auricular neurostimulation (tAN) as a therapeutic for opioid withdrawal and neonatal abstinence syndrome (NAS).

We hypothesize that tAN delivered for up to 60 minutes during peak withdrawal (1h before next morphine dose) will be safe, well tolerated and will decrease Finnegan withdrawal scores and shorten the length of morphine treatment compared with historical data.

Aim 1: Determine the safety and feasibility of auricular neurostimulation therapy in neonates with opioid withdrawal or NAS.

We hypothesize that auricular neurostimulation is safe and tolerable in both a single session, and 12-day treatment course. Furthermore, we believe target engagement can be validated by measuring stimulation-induced reductions in heart rate. Milestone: No adverse events of bradycardia (HR < 80 bpm), worsening of swallowing or feeding, skin irritation, or elevation of Neonatal Infant Pain Scores.

Aim 2: Demonstrate that auricular neurostimulation therapy in opioid withdrawing or NAS neonates reduces the Finnegan and/or WAT-1 scores from pre- to post-stimulation. We have used ear electrodes for taVNS in a similar stuy (#67997). However, in this prospective, open-label study we will use a novel, non-significant risk auricular neurostimulation device and ear electrodes to study 20 opioid withdrawing or NAS neonates at the Medical University of South Carolina. We aim to show a clinically-meaningful reduction in Finnegan scores, the routine assessment that includes 21 signs of withdrawal (Finnegan 1992). Alternatively, in infants who receive both opioids and benzodiazepine analgesics, we aim to show a clinically-meaningful reduction in Withdrawal Assessment Tool (WAT-1) scores, which is a validated, 11 item/12 point scale used to monitor opioid withdrawal in pediatric patients (Franck 2008). In the study, we will deliver up to 60 minutes of tAN 1 hour prior to each morphine administration, up to 4 times per day for up to 12 days. If morphine is weaned off at or before 10 days, a weaning phase for tAN will begin on the following day for 2 days: tAN Weaning Day 1: deliver tAN twice tAN Weaning Day 2: deliver tAN once We will assess each patient with standard Finnegan scores and/or WAT-1 before and after stimulation, and monitor use of morphine throughout the study. We expect a 25% reduction in Finnegan/WAT scores from before to after sessions of auricular neurostimulation.

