10.0 Study Design / Methods

After obtaining consent and describing this procedure to the parents and all members of the baby's care team, we will first deliver stimulation per our protocol in #67997 to determine the perceptual threshold. We will use the identical method for determining the intensity for PT, which has proven to be safe as in our taVNS study in infant feeding. We will start with 0.2mA with a 250µs, 5Hz in vagus and 100Hz in trigeminal nerve area, and gradually increase the intensity of the TENS unit until the baby can first feel something in their ear. We will use the facial expression change, fidgety movements to determine when the infants feel the stimulation, as in the taVNS study. This intensity will be recorded as the **perceptual sensory threshold (PT)**. The procedure is detailed below.

Determination of Perceptual Threshold

- 1. Electrode clip will be placed on the left tragus in an enrolled infant at rest. Starting at 0.2mA at 5Hz in vagus and 100Hz in trigeminal nerve area, we will deliver 5 seconds of pulses, and increase by 0.1mA until the perceptual threshold is achieved by observation of the infant's facial expression, fidgety movements. This will be termed the perceptual threshold.
- 2. We will decrease the microcurrent by $\sim 0.1 \text{mA}$ below the perceptual threshold and administer this as the taVNS treatment dose 1h before the morphine dose and before the infant is feeding, every 3h, for 60 minutes, up to 4 times per day. Current will then be held constant while pulse width and frequency will be set at $250 \mu \text{s}$ and 5 Hz in vagus area and 100 Hz in trigeminal nerve area, respectively.
- 3. Finnegan scores will be rated before and immediately after the taVNS treatment, and per usual clinical protocol. WAT-1 scores will also be rated during tAN treatment per usual clinical protocol.
- 4. Physiological data will be monitored continuously as measured by the echocardiogram (ECG).
- 5. Neonatal Infant Pain Scale (NIPS) data collected at beginning and the end of treatment session. The NIPS rating scale currently in use in the nursery is included in this submission.

taVNS Protocol

These studies will be conducted in the Shawn [name] Children's Hospital's Neonatal Intensive Care Unit (NICU).

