Participants will receive tAN stimulation to their left ear via electrodes attached to the ear. The stimulation intensity we will use for tAN will be ~0.1mA less than PT or each infant. We will recalibrate the PT daily, and then deliver that current intensity for each session that day administered every 3h, starting 1h before the morphine dose. The current will be on for 5 minutes, off for 10 seconds, for up to 60 minutes total each session, up to 4 times per day, for up to 12 days or until morphine is weaned off. If morphine is weaned off at or before 10 days, a weaning phase for tAN will begin on the following day for 2 days. tAN Weaning Day 1: deliver tAN twice. tAN Weaning Day 2: deliver tAN once.

The nurses will score the NAS using the Finnegan scale before and after the treatment. The Withdrawal Assessment Tool (WAT-1) will also be used to assess infant withdrawal symptoms before and after treatment in infants receiving benzodiazepines and opioids (Franck 2008, 2013). The WAT-1 is an 11 item/12 point scale to monitor withdrawal and is routinely performed by nurses 3 times per 12 hour shift with hands on care.

Prior to beginning the study, Drs. [name] and [name] will perform an in-depth in service with the charge nurses of the neonatal nurseries, a limited pool of 10 nurses. They will also in-service the neonatal nurses at their staff meetings to introduce them to the study, the rationale, the protocol and the equipment. Most nurses are familiar with ear electrode stimulation from the taVNS-paired feeding study conducted over the past 18 months.

A short developmental test, the STEP, will be performed while the infant is stil in the nursery and at the first neonatal high-risk developmental clinic (outpatient) follow-up visit.

Safety Monitoring

Prior to determination of the daily sensory threshold of the infant by the study coordinator or research assistant, an initial pain level will be recorded using the NIPS. The nurse or other staff may decrease the current intensity or stop stimulation entirely if the infant shows signs of distress or an increase in NIPS score >3 above baseline. As opioid withdrawing infants frequently have higher NIPS, we will only halt or adjust stimulation if the NIPS is 3 greater than their baseline. The nursing staff routinely measure and record the NIPS throughout the day. We will monitor the relationship of increased NIPS scores to the up to 60 minute stimulation period daily.

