Switching from left to right ear in case of left ear difficulties

Skin redness at the site of tAN attachment to the ear is possible after treatment, but is expected to be transient. In order to prevent injury to the skin in contact with the device, each day the left ear will be first examined for redness or other medical device placement prior to attaching the tAN earpiece. If there is skin redness or any emergent medical needs at the site of attachment to the ear prior to each day's treatment, we will switch the site of stimulation to the right ear until redness or emergent medical needs on left ear are resolved.

Estimated Difficulties, Limitations and Time Frames

Estimated Difficulties: Many of the initial difficulties surrounding taVNS in humans, such as feasibility, were accomplished in the taVNS-feeding pilot trial at MUSC by [name] and [name] that were approved by IRB 1. Electrode placement: The ear electrode is easy to fit to the infant's ear and much less likely to become dislodged due to head movement than the ear electrodes used in our taVNS infant feeding study. However, we will make sure the staff feel comfortable placing the electrodes and be on call to assist with electrode placement as needed for night shift nurses. The program will be either on or off switch for nurses to activate, but will have ability to decrease stimulation current as needed.

Limitations: Finnegan scores may not show a difference acutely with tAN treatment, but may lead to faster morphine weaning. However, this is not a randomized study, and we will not be able to determine if this is significant, as it will have to be compared with historical control data already collected and analyzed in Pro # 63667. Nevertheless, we will show feasibility and safety, and gather data for a larger randomized study.

Estimated Time Frames. We plan on completing enrollment in this study over a 6-12 month period.

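### The Safety Monitoring text states the rule for reducing or stopping stimulation in two consecutive sentences that do not agree on distress or on the NIPS cut-off

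*Protocol*

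**What the plan says.** The rule stands in the Safety Monitoring paragraph of section 10.0 of the protocol.

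- **First sentence.** It permits bedside staff to lower the current, and it equally permits them to "stop stimulation entirely if the infant shows signs of distress or an increase in NIPS score >3 above baseline". There are two triggers, joined by *or*, and the NIPS trigger is a strict inequality.
- **Second sentence.** It opens with a reason, "As opioid withdrawing infants frequently have higher NIPS", and then states a restriction: "we will only halt or adjust stimulation if the NIPS is 3 greater than their baseline". It names one trigger, does not mention distress, and gives the cut-off without an inequality sign.

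NIPS also has a role in the study's results. Section 4.0 lists it as a safety outcome, and section 1.0 includes a rise in NIPS among the events that the Aim 1 milestone requires to be absent.

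**The concern.** The two sentences govern the same action, reducing or stopping the current, and a nurse would read them together. They differ in two respects.

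1. **Distress as a trigger.** The first sentence treats distress as sufficient by itself. The word *only* in the second, taken literally, removes it unless NIPS has also risen by the stated amount.
2. **The cut-off.** The first sentence requires a rise of more than 3. The second refers to a rise of 3, which on its ordinary reading includes exactly 3.

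The study is a safety and feasibility trial in neonates, and bedside staff apply the rule session by session. Two people who follow the protocol as written could treat the same infant differently. The rule also decides which sessions are shortened or run at lower current, so it bears on how the tolerability data arise. This cannot be left to a statistical analysis plan: it is an instruction to staff, and the protocol is where it is stated.

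**Working it through.** The protocol gives no figure to reproduce, and no sample size or power calculation is involved. The check sets the two sentences side by side over every case they can meet.

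**Inputs**, all from Safety Monitoring in section 10.0:
- S1 (first sentence): action is permitted if there is distress, or if the NIPS rise is more than 3.
- S2 (second sentence): action is ruled out unless the NIPS rise is 3, read in the ordinary way as 3 or more.

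**Assumption:** NIPS is scored in whole points. The scale itself is not in the text at hand.

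**Definitions.** The sentences *contradict* where S1 permits action and S2 rules it out. They are *unclear* where S1 gives no permission but S2 does not rule action out. Otherwise they agree.

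Two states of distress and three bands of NIPS rise give 2 × 3 = 6 cases:

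| Distress | NIPS rise | S1 | S2, literal | Result |
|---|---|---|---|---|
| No | 2 or less | no permission | ruled out | agree |
| No | exactly 3 | no permission | not ruled out | **unclear** |
| No | 4 or more | permitted | not ruled out | agree |
| Yes | 2 or less | permitted | ruled out | **contradict** |
| Yes | exactly 3 | permitted | not ruled out | agree |
| Yes | 4 or more | permitted | not ruled out | agree |

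On the literal reading, four cases agree, one is a contradiction and one is unclear.

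**Do softer readings of S2 remove the problem?**
- If *only* is limited to the NIPS criterion and the cut-off still means 3 or more, the contradiction disappears. The case of no distress with a rise of exactly 3 stays unclear.
- If the cut-off is a loose repeat of more than 3 and *only* stays literal, the exactly-3 case without distress is settled. Distress with a rise of 2 or less is still a contradiction, and distress with a rise of exactly 3 becomes one.
- If both softer readings are adopted together, all six cases agree.

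Full agreement therefore needs both rereadings, and the text directs neither. These readings are not equally plausible, so a tally of them would measure nothing about risk.

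**The case against.** The strongest reply is that the second sentence should be read in its context. Its opening clause explains why a raised NIPS is judged against the infant's own baseline. It gives no reason to disregard distress, which the sentence before has just listed separately. On that view *only* qualifies the NIPS criterion, and the direct contradiction goes away. The exactly-3 case is then not a contradiction either: the first sentence grants permission and forbids nothing, and the second sentence's cut-off, coming straight after the first, may simply repeat it loosely. Section 10.0 also provides in-service training for the charge nurses before the study starts.

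Much of this stands. The NIPS-only reading is plausible, and it lowers the weight of the point. It does not make the written rule consistent: the scope of *only* has to be inferred, and the cut-off is still worded in two ways. No other section settles either question, and the protocol does not say that the training covers them.

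A reader might also infer three further defects, which the documents do not support:
- **A third competing rule.** The Estimated Difficulties text says that the device program "will have ability to decrease stimulation current as needed". That describes what the device can do, not when staff should act.
- **A missing heart-rate trigger.** Section 1.0 has the milestone "No adverse events of bradycardia (HR < 80 bpm" as an adverse event to be absent. It is not a rule for stopping, and the Safety Monitoring paragraph does not contradict it.
- **An undefined baseline.** The same paragraph says, just before the rule, that "an initial pain level will be recorded using the NIPS", which is the natural referent. Step 5 of the threshold procedure also has "Neonatal Infant Pain Scale (NIPS) data collected at beginning and the end of treatment session", but that does not displace it.

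**Conclusion.** The point holds as an inconsistency of wording in a bedside safety rule. Read literally, the two sentences contradict each other on whether distress permits action when NIPS has not risen by the stated amount, and they leave a rise of exactly 3 without distress unclear. That is two of six cases, assuming whole-point scoring and a literal *only*. If *only* is limited to the NIPS criterion, at most the exactly-3 case remains.

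A reader might infer that infants in distress would go on being stimulated, or that the safety results are compromised. The documents support neither. The first sentence expressly allows staff to act on distress, nothing in the protocol says how often the disputed cases occur, and no effect on an endpoint can be calculated. The point is therefore a should-fix clarification and not a fault that undermines the study. No view is taken here on which cut-off or trigger is clinically right.

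**What to change.** Reconcile the two sentences under Safety Monitoring into one rule that:

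1. uses a single NIPS cut-off, written so that it is plain whether a rise of exactly 3 is included; and
2. states whether *only* limits the NIPS criterion alone or also excludes distress as a separate trigger.

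The investigator sets the clinical values. The cost is a wording change to one paragraph and the same wording in the staff in-service. It needs no new assessment, data item or change to the sample.

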4.0 Study Endpoints

Safety Outcomes: 1) Skin irritation, assessed by staff daily. 2) NIPS pain scores recorded during treatment.

Efficacy Outcomes: 1) Finnegan scores before and after tAN will be recorded at each session or WAT-1 scores will be recorded with hands on care . 2) Duration of morphine weaning. 3) Length of stay We will also collect data on developmental outcomes from a short motor test in the nursery and from routine clinic visits to the NICU high-risk follow-up clinic up to 24months.

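### The ear examination and ear-switch rule run once a day, before the day's treatment, although up to four 60-minute sessions may be given daily, so later sessions can start with no required skin check

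*Protocol*

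**What the plan says.** Four parts of the protocol bear on this.

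- **Skin outcome (Section 4.0).** The first safety outcome is "Skin irritation, assessed by staff daily". No time of day and no link to sessions is given.
- **Ear examination and switch (Section 10.0, on switching from left to right ear).** The text first grants that "Skin redness at the site of tAN attachment to the ear is possible after treatment, but is expected to be transient". To protect the skin, "each day the left ear will be first examined for redness or other medical device placement prior to attaching the tAN earpiece". The trigger for changing ears reads "If there is skin redness or any emergent medical needs at the site of attachment to the ear prior to each day's treatment". Stimulation then moves to the right ear until the left has resolved. Only the left ear is named for examination.
- **Schedule (Section 10.0).** The perceptual threshold is set once a day, and staff then "deliver that current intensity for each session that day administered every 3h, starting 1h before the morphine dose". Stimulation runs "for up to 60 minutes total each session, up to 4 times per day, for up to 12 days".
- **Rules within the day (Section 10.0, Safety Monitoring).** "The nurse or other staff may decrease the current intensity or stop stimulation entirely if the infant shows signs of distress", or if the NIPS pain score rises past a set margin over baseline. Skin is not named as a ground.

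Other measures are tied to the session: "Finnegan scores will be rated before and immediately after the taVNS treatment", and NIPS is collected at the start and end of each session.

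**The concern.** The protocol expects redness to follow a session and then fade, yet its only look with a fixed place in the schedule comes before the day's first session. An ear reddened by the first session can be used again about two hours later without anyone being required to inspect it. Redness that comes and goes within the day need not be seen at any required look.

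This is a safety and feasibility trial in newborns and infants. Skin irritation is a listed safety outcome, and Section 1.0 gives it as the only side effect reported for the device. Section 15.0 does not expect irritation from up to 60 minutes of current, but it does not address repeated sessions. Four such sessions come to 4 × 60 = 240 minutes a day, with the left ear as the default site.

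**Working it through.** The protocol gives no figure of its own here, so the check is a reading of the text plus a count.

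**Inputs.** From Section 10.0: up to 4 sessions a day, up to 60 minutes each, every 3 h, up to 12 days; if morphine is off by day 10, two weaning days with 2 sessions and then 1; one ear examination a day. From Section 4.0: one skin assessment a day at an unstated time.

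**Sessions with no required skin check before them** = sessions − required looks that precede a session. *One look* treats the Section 4.0 assessment as the same look as the Section 10.0 examination, or as one that precedes no session. *Two looks* assumes it is separate and falls before another session that day, where there is one.

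| Course | Sessions | Unchecked, one look a day | Unchecked, two looks a day |
|---|---|---|---|
| 4 a day, 12 days | 4 × 12 = 48 | 48 − 12 = 36 (75%) | 48 − 24 = 24 (50%) |
| Morphine off at day 10, then wean | 4 × 10 + 2 + 1 = 43 | 3 × 10 + 1 + 0 = 31 (72%) | 2 × 10 + 0 + 0 = 20 (47%) |
| 2 a day, 12 days | 2 × 12 = 24 | 24 − 12 = 12 (50%) | 24 − 24 = 0 |

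**How long redness must last to matter.** The protocol gives no duration. Assume 60-minute sessions starting at 0, 3, 6 and 9 h, at the same clock times each day. They end at 1, 4, 7 and 10 h.

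- Gap to the next session on the same day: 3 − 1 = 2 h. Redness after sessions 1 to 3 that lasts about 2 h or more is still present when the next session starts.
- To be seen at the next day's examination, at 24 h, redness must last 24 − 1 = 23 h, 24 − 4 = 20 h, 24 − 7 = 17 h or 24 − 10 = 14 h after sessions 1 to 4. This ignores any renewal by later sessions.
- If the Section 4.0 look is separate and falls right after the last session, at 10 h, the durations needed are 10 − 1 = 9, 10 − 4 = 6, 10 − 7 = 3 and 0 h. A look placed there helps recording but precedes no further session that day, so the one-look column still applies.

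Redness shorter than the gap may be missed. Redness longer than the gap may be restimulated. Redness after session 1 lasting, say, 5 h is present at the start of session 2 and, unless renewed, has gone by the next fixed look under either timing.

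**The case against.** **The examination may already be per session.** It is placed before the earpiece is attached. If the earpiece comes off after every session, that could mean every attachment. This reading is possible, but both sentences carry daily wording, which favours once a day. If a per-session look was intended, the change only states it.

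**Staff will see the ear anyway.** Nurses are trained on the device, score the infant around each session, and may lower or stop the current. The investigators review adverse events. All this stands: nothing forbids acting on or recording a red ear. The point is only that no stated rule requires a look, a record or a change of ear.

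**The daily rule has a logic.** The ear is chosen, the threshold set, and that current used all day. A switch partway through the day would apply a current calibrated on the other ear, so the margin of about 0.1 mA below threshold would no longer be assured. This is right, and the fix must include a new threshold.

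**Looking has its own cost.** Section 3.0 says that adhesive surrounds the electrodes. Lifting it from a newborn's ear only to inspect could itself irritate the skin. This also stands and limits what should be asked.

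**A stronger reading to avoid.** A reader might infer that missed redness makes the Aim 1 milestone of no skin-irritation events easier to meet. The documents do not support that. Section 10.0 treats transient redness as possible, Section 15.0 lists irritation and redness as separate terms, and nothing says that brief redness counts as an irritation event. Nor do they support any statement of how often redness occurs or that injury will follow.

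**Conclusion.** The gap is real and worth correcting. As written, a skin check is required once a day before treatment, and nothing stated prevents a reddened ear from being stimulated again the same day. The size is up to 36 of 48 sessions over a full course, 24 of 48 if the Section 4.0 assessment is a separate look before another session, and fewer with fewer sessions a day (12 or 0 of 24 at two a day). These counts describe the schedule of checks, not harm.

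The conclusion rests on the daily reading of the examination sentence, which the wording favours without settling. The practical consequence depends on how long redness lasts, which the protocol does not give. Confidence is therefore moderate.

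**What to change.** **Section 10.0, on switching ears.** Replace the daily wording in both sentences so that the ear about to be stimulated, left or right, is examined before the earpiece is attached for each session. If it is red, switch ears. If both are red, hold the session. After any switch within a day, redetermine the perceptual threshold on the new ear before stimulating.

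**Section 4.0.** Record skin findings, with ear and session number, whenever the earpiece is removed after a session. If it stays on between sessions, inspect the visible skin and do not lift the adhesive solely to look.

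**Cost.** Per infant, up to 48 − 12 = 36 added brief looks before sessions and up to 48 end-of-session records, by staff already at the bedside. There would also be an occasional repeat threshold determination, an occasional held session, and possibly a higher reported irritation rate.

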Drs. [name] and [name] have an IRB-approved protocol (#67997) for studying the use of transcutaneous auricular vagus nerve stimulation (taVNS) for improving oromotor function in newborns. In our taVNS protocol we use an ear clip electrode to devlier the stimuatlion, but this electrode has the disadvantage of becoming displaced with head turning, burping etc. Therefore, we propose to use Spark Biomedical company's non-invasive, auricular neurostimulation device in this study to treat opioid withdrawal symptoms of babies with NAS. This device will be placed in the ear (similar to a hearing aid) and will target trigeminal and vagal nerve branches. Stimulation will be delivered transcutaneously via a hydrogel interface similar to the standard EMG and EKG leads we currently use in #67997. This device has proven to be safe across many indications with the only side effect being skin irritation. Spark Biomedical is curenlty working on FDA clearance for adult opioid withdrawal based on predicate devices (K173861, DEN170018). This product will be regulated as a Class II medical device by the FDA.

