Based on evidence that auricular neurostimulation reduces opioid withdrawal severity in adults, our team's experience in an ongoing clinical study of auricular neurostimulation to improve oromotor function in newborns (#67997), we propose to use an auricular neurostimulation device, specifically to fit newborns, to treat opioid withdrawal and NAS patients.

Device Description. The "Roo" (**Figure 2C**) is a non-invasive, battery-operated, prescription device designed to transcutaneously stimulate nerves on and/or around the auricle. Electrical stimulation is delivered through an ergonomically designed Earpiece (**Figure 2A**). The Earpiece is a disposable component that includes a single flexible circuit board with over molded silicone. The Earpiece contains four embedded hydrogel electrodes (**Figure 2B**), for stimulation of the ABVN and auricular temporal branch of trigeminal nerve nerve (ATN). To ensure sufficient skin-contact, the surface surrounding the hydrogel electrodes is covered with a medical grade adhesive. The system includes an External Pulse Generator (EPG, **Figure 2A**) that produces a current-controlled, biphasic stimulation output. The EPG and the Earpiece are connected to each other via a cable. The Roo device is based on the adult Phoenix System, but will fit neoantes and infants.

[figure not shown]

Figure 2. (A) Phoenix System (adult), External Pulse Generator and Earpiece. (B) Phoenix System, Patient contacting side of the Earpiece. (C) Roo device, fit for infant use.

The earpiece is worn around and inside the ear. The four electrodes are positioned to stimulate three key dermatome regions (Figure 3, below). These regions are adjacent to several cranial nerves (V, VII, IX, X) and occipital nerves. In particular, the electrodes are located in the concha cymba (Figure 3, *Region 1*), on the temporomandibular join region, just anterior to the tragus (Figure 3, *Region 2*), and behind the auricle (Figure 3, *Region 3*).

Initial use. During first use, [name] will program the device with the study team and set the stimulation intensity to just below the perceptual threshold.

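### The ear-switching rule sends stimulation to the right ear without regard to the state of that ear's skin

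*Protocol*

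**What the plan says.** Section 10.0 makes the left ear the standard site of stimulation. Its paragraph on switching ears opens with a warning: "Skin redness at the site of tAN attachment to the ear is possible after treatment, but is expected to be transient". It then gives its purpose, "In order to prevent injury to the skin in contact with the device", and the check that serves it: "each day the left ear will be first examined for redness or other medical device placement prior to attaching the tAN earpiece". If redness or an emergent medical need is found at the attachment site before the day's treatment, the instruction is that "we will switch the site of stimulation to the right ear until redness or emergent medical needs on left ear are resolved".

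Skin irritation also appears in other sections:

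- Section 1.0 describes the device's safety record "with the only side effect being skin irritation". The Aim 1 milestone requires no adverse events of several kinds, among them "worsening of swallowing or feeding, skin irritation, or elevation of Neonatal Infant Pain Scores".
- Section 3.0 (Device Description) notes that "the surface surrounding the hydrogel electrodes is covered with a medical grade adhesive".
- Section 4.0 lists, first among the safety outcomes, "Skin irritation, assessed by staff daily".
- Section 15.0 does not expect irritation with sessions of up to 60 minutes.

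**The concern.** The rule is meant to protect whichever skin the device touches. Once stimulation has moved to the right ear, that is right-ear skin, yet the check and the condition for moving back still name only the left ear. An infant whose left ear is unavailable and whose right ear has become red would, on the written rule, go on being stimulated on the red ear until the left one recovers.

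What is at stake is avoidable skin injury in neonates and infants who cannot say that something hurts. The point is not that events would be missed or miscounted, or that any efficacy or safety analysis would be biased.

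**Working it through.** No arithmetic applies, because the protocol gives no rate of redness for either ear. The check is to read the rule as a decision rule, list its inputs, and follow each case.

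**Inputs the rule uses.** There is one: whether the left ear is clear. The examination is of the left ear, the only action is a move to the right ear, and the only condition for ending that move is recovery of the left ear. The right ear's state is not an input.

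**Outcome by case.**

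| Left ear | Right ear | Where the rule puts the earpiece | Consistent with the rule's purpose? |
|---|---|---|---|
| Clear | Clear | Left | Yes |
| Clear | Red | Left | Yes |
| Unavailable | Clear | Right | Yes |
| Unavailable | Red | Right | No |

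Only the last row fails, and the failure ends when the left ear recovers.

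**Is the last row foreseeable?** Yes, on the protocol's own account. After a switch, the right ear takes over the same schedule: up to 60 minutes a session, up to 4 sessions a day, within a course of up to 12 days. The same adhesive earpiece is in use, and the protocol says that redness can follow treatment at the attachment site. The left ear need not be red for this to arise, because an emergent medical need there also triggers the switch.

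**Does another section supply the missing instruction?**

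- *Section 4.0, daily skin assessment.* It names no side, so right-ear redness would probably be recorded. It attaches no action to the finding.
- *Section 1.0, Aim 1 milestone.* It sets the safety target but gives no bedside instruction.
- *Section 10.0, Safety Monitoring.* Staff may reduce or stop stimulation for distress or a rise in the NIPS pain score. Skin state is not among the stated grounds. I read the NIPS threshold as governing pain scores, not as forbidding a stop for redness.
- *Section 13.0.* The undertaking to minimize risks is general.

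These provisions allow staff to withhold a session. None tells them to.

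**The case against.** The strongest reply is that this reading turns silence into an instruction. The paragraph is a short contingency for trouble with the left ear, written for nurses who are trained before the study starts. Its purpose names no side, and its trigger refers to the attachment site without saying which ear. It says that the left ear is examined first, which could imply that the right is examined next. Staff who move an earpiece because of redness would hardly put it on another red ear. They will see right-ear redness at the daily assessment and may withhold a session, because the session and day limits are ceilings. The scenario needs two things on the same day, redness is expected to be transient, and nothing in the trial's conclusions depends on it.

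Much of this stands. Sensible staff may well do the right thing, the situation may be rare, and the analysis is untouched. Those points limit the weight of the finding.

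They do not repair the text. The trigger, read for either ear, still leads only to the right ear, so it achieves nothing when the right ear is already in use. No second examination is stated, and even if one were implied, no action follows from it. The paragraph is also not merely silent: it gives a positive instruction to use the right ear and fixes when that instruction ends, with reference to the left ear alone.

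**Conclusion.** The concern holds, as a minor point. With the left ear unavailable and the right ear red, the rule as written puts the earpiece on red skin, against its own stated aim.

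Confidence is high about what the text says and omits. How often the situation would occur, and whether staff would follow the letter of the rule when it did, cannot be known from the document. The gap exists only on days when both conditions hold. Since the protocol expects redness to pass quickly, and does not expect irritation from sessions of this length, such days may be few.

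**What to change.** Amend the ear-switching paragraph in section 10.0 along these lines:

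- Before attaching the earpiece, examine the ear that is about to carry it.
- Apply no stimulation to an ear that is red or otherwise unavailable.
- If neither ear is suitable, withhold tAN and refer the infant to the clinical team.

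The cost is about one sentence of protocol text and a few seconds per check. The downside is an occasional withheld session, which sections 6.0 and 10.0 already permit because they set upper limits on session length, sessions per day and days of treatment.
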